8 SAFETY ASSESSMENT

8.1 Definitions for safety assessment

Adverse event

Adverse event (AE) is any untoward medical occurrence in a study subject, which is not necessarily related to the use of the medicinal product. An adverse event may be any undesirable and unexpected manifestation (including changes in laboratory findings), a symptom or a disease that occurs in temporal association with the administration of the medicinal product (to the study

subject), regardless of whether it is related to the administration of the medicinal product (to the study subject) or not;

Any medical condition that is present at the time of patient's screening, but does not worsen during the study, must not be registered as an AE. However, in case of deterioration of this medical condition at any time during the study, it shall be registered as an AE.

Medical interventions, such as surgeries, diagnostic and therapeutic procedures, are not AEs; however, they are measures undertaken to treat the respective medical condition, and may therefore be registered as AE treatment, unless they are elective.

Deviation of laboratory findings from normal

Any deviation of a laboratory finding from normal, which has appeared for the first time or the severity or frequency of which has increased compared to baseline, and which meets at least one of the following criteria, shall be recorded as an AE:

- Requires a therapeutic intervention or a diagnostic procedure;
- Leads to discontinuation of the IMP;
- Is accompanied by complaints or symptoms, or causes them;
- Is assessed by the investigator as "clinically significant".

In any doubt as to whether the observed clinical event is an AE, the same shall be registered as an AE.

Adverse reaction

Adverse reaction (AR) within a clinical trial of a medicinal product (original/generic) or its evaluation for new use, especially if the therapeutic doses of the medicinal product have not been established, adverse reactions to a medicinal product must encompass all adverse and unpredictable responses to administration of any dose of the medicinal product. The term "response to administration of the medicinal product" implies that there is at least an assumed probability of a causal relationship between the administration of the medicinal product and the adverse reaction, i.e. the correlation cannot be ruled out.

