8.2 AE detection and documentation

The identification and registration of AEs begins from the time of signing the informed consent and continues until the end of the given patient's participation in the study.

AE identification and registration starts from the moment of drug administration and continues until the end of the patient's participation in the study.

The AEs that occur between the screening and drug administration and that are not SAEs must be recorded as medical history.

All AEs occurring from the moment of drug administration, which are reported by the patient or identified during the follow-up, physical examination and other diagnostic procedures, shall be registered in the AE Report Form, which is a structural constituent of the eCRF.

Laboratory findings will be evaluated during screening and throughout the study.

Information on any AEs observed during the study period, starting with the first administration of the investigational product and up to the end of investigational product use is documented in medical records/outpatient card of the patient and under the AE section in the eCRF. All AEs must be documented, regardless of their severity or causality with the investigational medicinal product.

The following events **must** be classified as AEs:

- exacerbations/flare of pre-existing conditions;
- increase in incidence or severity (intensity) of diseases or previously observed episodic events;
- any disease(s) detected or diagnosed after the onset of treatment with the investigational medicinal product, even if it was possible for the disease(s) to be present before the start of patient's participation in the study;
- any prolonged and/or persistent illnesses or symptoms present at baseline, the severity of which increased after the patient joined the study;
- new signs or any increase in severity of signs and symptoms of diabetes that required immediate treatment, hospitalisation, surgery and/or any other intervention;
- any clinically significant abnormalities of laboratory results or findings of other tests occurring after the onset of treatment with the investigational product, or any such baseline abnormalities, the severity of which increased in a setting of treatment with the investigational medicinal product.

The following events **shall NOT** be classified as AEs:

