Information to be recorded includes the event type, AE onset date, investigator's assessment of AE severity and AE association with the IMP, AE cessation (resolution) date, AE seriousness, measures taken, and AE outcome.

All AEs shall be monitored until they are adequately resolved.

During and after the subject's participation in the study, the investigator (medical institution) must ensure that the subject is provided with necessary medical care in case of any study-related adverse events, including clinically significant changes in laboratory findings. The Investigator (medical institution) must inform the study subject about any concurrent diseases requiring medical attention, which have become known to the Investigator.

Assessment of AE severity

AE severity (intensity) indicates the extent to which the AE affects the patient's daily activity. AE severity degree will be determined according to NCI CTCAE criteria developed by the US National Cancer Institute (version 5.0) (in each item, a semicolon means "or") Table 8.2.2.

Table 8.2.2. AE severity degree according to NCI CTCAE (version 5.0)

Severity degree 1	Mild; no symptoms or minor symptoms; only clinical or diagnostic observations; no intervention is required
Severity degree 2	Moderate; requires minimal, local or non-invasive intervention (e.g., tamponade, cauterisation); restriction corresponds to Instrumental Activities of Daily Living (ADL*)
Severity degree 3	Severe or clinically significant but not life-threatening; hospitalisation or continuation of hospitalisation is required; restriction in Self Care Activities of Daily Living (ADL**)
Severity degree 4	Life-threatening condition; immediate intervention is required
Severity degree 5	Death associated with AE

Activities of Daily Living (ADL):

*Instrumental Activities of Daily Living include cooking, buying food or clothing, using the phone, handling money, etc.

**Self Care Activities of Daily Living include taking a bath, dressing and undressing, eating independently, using the toilet, taking medication and not being bedridden.

The terms "serious" and "severe" are not synonymous. A severe AE (3rd or 4th severity degree) must not always be considered serious. For example, a white blood cell count of 1000 to 2000 / mm³ shall be considered a degree 3 (severe) AE, but such an AE may not be recognised as serious. A benchmark for submitting information to regulatory authorities is the seriousness (but not severity) of an AE.

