Assessment of causal relationship between the AE and the investigational product

During the assessment of causal relationship, the Investigator must take into account the possible aetiology of the observed AE/AR, which may be related to the administration of the investigational medicinal product, concomitant medications, the course of the underlying disease, comorbidities, procedures performed during the study, and other causes. Of all the possible causes, the Investigator must identify the single cause with the likeliest causality to the event in question. During assessment of causality in case of a serious AE, the report shall provide the rationale for the Investigator's judgement. This rationale has to include all of the available facts supporting the judgement, including laboratory results and other diagnostic findings.

- **Verified causality.** The clinical event and/or changes in laboratory results have temporal connection with the use of the medicinal product and cannot be attributed to a comorbidity or to other medicinal products or chemical substances. The response to product discontinuation must be clinically significant. If necessary, the event has been confirmed by a rechallenge.
- **Probable causality.** The clinical event and/or changes in laboratory results have temporal connection with the use of the medicinal product and are unlikely to be attributed to a comorbidity or to other medicinal products or chemical substances and a clinically distinctive response to discontinuation of the product has been observed.
- **Possible causality.** The clinical event and/or changes in laboratory results have temporal connection with the use of the medicinal product, but they are also attributable to existing comorbidities or to other medicinal products or chemical substances. The results of rechallenge may be negative or ambiguous.
- **Dubious causality.** The clinical event and/or changes in laboratory results may have temporal connection with the use of the medicinal product, but other medicinal products, chemical substances or comorbidities are a more likely explanation for the event.

- **No causality.** The clinical event and/or changes in laboratory results are *beyond any reasonable doubt* unrelated to the use of the product in question due to lack of substantiated temporal connection between the drug and the AE and/or implausibility of such a connection.

Categories of AE outcomes and their definitions

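### Section 8.2 asks for the single likeliest cause of each adverse event, while Section 8.1 counts as an adverse reaction any event whose link to the product cannot be ruled out; nothing says which test decides

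*Protocol*

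**What the plan says.** Section 8.1 defines an AR by a low threshold. It is enough that "there is at least an assumed probability of a causal relationship between the administration of the medicinal product and the adverse reaction", which the text glosses as "i.e. the correlation cannot be ruled out".

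Section 8.2, under its heading on the causal relationship with the investigational product, lists possible causes: the product, concomitant medication, the underlying disease, comorbidities, study procedures and others. It then says that "the Investigator must identify the single cause with the likeliest causality to the event in question". Five grades follow: verified, probable, possible, dubious and no causality. For a possible event there is a temporal link, "but they are also attributable to existing comorbidities or to other medicinal products or chemical substances". For a dubious event a temporal link may exist, but "other medicinal products, chemical substances or comorbidities are a more likely explanation for the event". Only the last grade excludes the product; such an event is, beyond reasonable doubt, "unrelated to the use of the product in question due to lack of substantiated temporal connection between the drug and the AE" or because such a connection is implausible.

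Section 8.2 also has the following recorded for each event: "investigator's assessment of AE severity and AE association with the IMP". It adds: "All AEs must be documented, regardless of their severity or causality with the investigational medicinal product".

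Section 8.3 has the investigator decide whether each SAE is related to the product, with no cut-off on the five grades. Section 4.1 lists AR incidence and SAR frequency among the safety endpoints. Section 8.1 gives SAR and SAE one shared definition, which requires seriousness but no causal link.

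**The concern.** A link that cannot be excluded is a much weaker condition than being the likeliest cause. The protocol uses the first to define an AR and the second to instruct the person who makes the call. It does not say which prevails, or whether the named cause or the recorded grade determines AR status.

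AR incidence is a safety endpoint. In Section 8.3 the sponsor's 7-day and 15-day reports to authorities concern SAEs related to or associated with the product. In Section 6.3.21 a serious event that may be related to the product, and so be an AR, can bring forward the Independent Safety Committee's review. The study is open-label and single-arm, so no control group would show a shift in attribution.

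A statistical analysis plan could map recorded grades to ARs for the tables. It could not undo a relatedness call already made at the site under a most-likely-cause instruction, nor could it govern reporting in real time. That is why this conflict has to be settled in the protocol.

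**Working it through.** The protocol gives no expected AR rate and no share of events per grade, so there is no stated figure to reproduce. The check sets the two tests against each grade as Section 8.2 defines it.

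| Grade (8.2) | Link ruled out? | AR under 8.1? | Can the product be the single likeliest cause? |
|---|---|---|---|
| Verified | No | Yes | Yes |
| Probable | No | Yes | Yes |
| Possible | No | Yes | Only if no other cause is ranked first |
| Dubious | No | Yes | Never, because another cause is likelier by definition |
| No causality | Yes | No | No |

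Let V, P, Q and D be the numbers of events graded verified, probable, possible and dubious. Let k, between 0 and 1, be the share of possible events for which the investigator ranks another cause first.

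- AR count under Section 8.1: V + P + Q + D.
- AR count if the single-cause choice decides: V + P + (1 − k)Q.
- Shortfall: D + kQ.

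Three readings follow.

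1. **The single-cause choice decides AR status.** All D dubious events are lost, with kQ of the possible ones. The shortfall lies between D (k = 0) and D + Q (k = 1).
2. **The Section 8.1 threshold is applied to the recorded grade.** Nothing is lost and the shortfall is 0.
3. **The shared SAR/SAE definition in Section 8.1 is read literally.** Every SAE is a SAR whatever its grade. The SAR count then equals the SAE count, which is higher than a count restricted to SAEs that meet the AR definition whenever any SAE is graded no causality.

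D, Q and k are not in the protocol. The shortfall can therefore be bounded only in symbols, from 0 to D + Q. The total numbers of AEs and SAEs do not depend on the causality call.

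**The case against.** The strongest defence is that the two instructions can coexist. One names the leading aetiology and the other grades the link to the product. The dubious grade exists precisely for events with a likelier explanation, so naming that explanation does not erase the grade. The association with the product is recorded for every AE, and the only definition of an AR is the one in Section 8.1. Applied to the recorded grade, that definition loses nothing. This stands as a possible reading, and it is why the undercount is a risk and not a stated rule. It does not remove the conflict: the single-cause sentence is mandatory, it opens the very assessment that yields the grade, and nothing confines it to a descriptive role.

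A reader might go further and infer that possible and dubious events drop out, so that both AR and SAR rates read low. The protocol does not support that:

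- No section says that events of either grade are excluded.
- The two grades differ. A possible event is also attributable to something else; its definition does not make the other cause likelier, or even equally likely.
- For SARs the direction is unsettled, because the shared definition could push the rate up.

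The effect on reporting is also limited. Every SAE goes to the sponsor within 24 hours regardless of causality, the investigator must give the reasoning and supporting facts for a serious event, and the Ukrainian 7-day rule covers suspected reactions. The investigator's choice of cause therefore does not hide a serious event from the sponsor. It can still affect whether the event is handled as related.

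Finally, the choice of grades to tabulate as related is often left to the statistical analysis plan. That gap alone would be no finding. The finding is that two current sections of the protocol set different tests.

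**Conclusion.** The point holds in a conditional form. Sections 8.1 and 8.2 apply different tests to the same judgement, and Section 8.3 then asks for a relatedness call without saying which test governs. If investigators let the single likeliest cause decide, AR incidence is understated by D + kQ, and related SAEs may be under-reported as such. If they grade the link and apply Section 8.1, there is no understatement. The conclusion assumes that the grades are used as defined. The documents do not show which practice sites will follow or how many events fall in each grade, so no numerical size can be given.

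A low SAR rate should not be claimed. The accurate statement is that SAR frequency is not uniquely defined: it may equal the SAE frequency or a causally restricted subset. AE and SAE totals stand. This is a defect worth correcting because it touches a listed safety endpoint and the handling of serious events, and because the repair is cheap.

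**What to change.** 1. In Section 8.2, delete the single-cause sentence, or keep it as a descriptive field on the most likely aetiology and state that this field does not decide relatedness.
2. State in Sections 8.2 and 8.3 that AR status and the relatedness call on SAEs follow the Section 8.1 threshold applied to the recorded causality grade. Verified, probable, possible and dubious then count as related, and only no causality counts as unrelated.
3. In Section 8.1, separate SAR from SAE and define a SAR as an SAE that also meets the AR definition, so that the SAR endpoint in Section 4.1 has one meaning.

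The cost is protocol wording, the eCRF completion guide and site training. The downside for the sponsor is a somewhat higher, less favourable AR rate than a most-likely-cause reading would give.

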8.3 Reporting of SAE/SAR cases

Any SAE shall be reported to the Study Sponsor within 24 hours after the Investigator first became aware of this SAE. When an SAE develops, the Investigator fills in the SAE registration form and determines whether the SAE is related to the investigational product and sends the completed form to the Sponsor by email. The original SAE form and the letter with confirmation of form receipt by the Sponsor must be stored. The fact of the SAE must be recorded in the eCRF. Sponsor has the right to urgently request additional information about the SAE from the Investigator for reporting to the health authorities.

After the initial urgent notification, a detailed written notification shall be submitted as soon as possible. The initial and subsequent reports must identify study subjects by the unique code assigned to them, and not by the subjects' names, personal identification numbers and/or addresses.

In case of hospitalisation of the patient in connection with an SAE development, a copy of hospital discharge summary must be sent to the Study Sponsor by email as soon as possible.

The Study Sponsor or his/her authorised representative shall be responsible for telephone or fax notifications of unexpected or life-threatening SAEs related to the use of the investigational product (in the form of urgent reports) to the relevant bodies and competent authorities within 7 calendar days of receipt of information about the SAE. The Study Sponsor or his/her authorised representative shall report any other significant SAEs associated with the use of the investigational product to the relevant competent authorities, investigators and the Independent Ethics Committee by providing a written safety report within 15 calendar days of receipt of information about the SAE.

In Ukraine, within 7 calendar days from the time of awareness of any suspected unexpected serious adverse reactions related to the investigational medicinal product, which led to death of or were life-threatening to a study subject, the Sponsor shall immediately record and report such

occurrence(s) to SEC MoH of Ukraine and the Ethics Committee. Additional information in this connection shall be provided to SEC MoH of Ukraine and the Ethics Committee within the next 8 calendar days. The notification of a suspected unexpected serious adverse reaction shall be compiled in accordance with Order of the Ministry of Health of Ukraine No. 690 of 23/09/2009, as amended.

In addition to the notification of deaths, the investigator shall provide any additional information at the request of the regulatory competent authority (e.g. autopsy report and final medical reports after they have been duly completed in accordance with the legislation of the country where the study is conducted – Ukraine).

8.4 Reporting requirements after the end of treatment with the investigational product.

In case the Investigator receives information about any AE that has occurred at any time after the patient has completed treatment with the investigational medicinal product, and if there is sufficient evidence to suggest a relationship between this event and use of the investigational product, the Investigator must notify the Sponsor.

9. STATISTICS

9.1. Contents of statistical analysis

Subjects who withdrew during the screening phase are not counted in the efficacy and safety analysis since they have not received any administration of the investigational medicinal product (IMP).

Subjects who have not received a full IMP course are included in the safety analysis, but are not included in the efficacy analysis.

Subjects who discontinued from the study after completing IMP administration during the follow-up period are included in the efficacy and safety analysis. The data of such subjects are evaluated by parameters that may be analysed at a certain time point. The dropped data are not analysed.

Subjects who received at least one dose of the IMP but withdrew from the study prematurely are included by the Investigator in the tolerability analysis of the investigational product.

Statistical analysis:

Populations for statistical analysis:

ITT (Intention-to-treat population) includes all study subjects who received the investigational product at least once. The data obtained from this sample will be used for the safety analysis.

PP (Per Protocol) includes all patients who complied with the protocol requirements. This population includes all patients who received full protocol therapy, who underwent all scheduled visits, and did not have significant protocol deviations. The data obtained from this sample will be used for analysis by efficacy criteria.

The main efficacy analysis is performed on the PP population, and the additional, confirmatory analysis is performed on the ITT population (all subjects who received ≥ 1 dose and who meet the inclusion criteria, and for whom efficacy can be established).

Plan of statistical analysis of CS results

Statistical analysis is performed by a qualified biostatistician, a third party contracted by the Sponsor. Statistical analysis includes the following:

- description of patients enrolled in the study;
- the number of drop-out subjects;
- the number of adverse events;
- efficacy analysis in the group;
- tolerability assessment in the group;
- safety assessment in the group;
- analysis of pharmacokinetic data;
- statistical inferences.

9.2 Sample size assessment

According to European guidelines (Guideline on the clinical investigation of human normal immunoglobulin for subcutaneous and/or intramuscular administration [SCIg/IMIg]), the number of patients must be greater than 40, with previously verified humoral and combined primary immunodeficiencies, to ensure a minimum of 80 % statistical power for rejecting the null hypothesis when using a one-tailed test and a significance level of $p = 0.01$. For the primary

efficacy variable, the null hypothesis H_0 is that the frequency of serious bacterial infection cases is 1.0 or greater per year. The alternative hypothesis H_1 is that the frequency of serious bacterial infection cases is less than 1.0 per year. The null hypothesis is rejected if the upper limit of the 99 % confidence interval is less than 1.0 case of serious bacterial infection per patient per year.

The study must provide at least an 80 % probability of rejecting the null hypothesis regarding the number of serious bacterial infection cases ≤ 1.0 per 1 patient over the treatment period using a one-tailed test and a type I error according to the chosen significance level of $p \leq 0.01$.

Taking into account possible subject withdrawals at different phases, 56 subjects are enrolled in the study to achieve a required sample size.

Since patients were distributed across cohorts, the required number of patients in each cohort was established in accordance with the recommendations of the U.S. Department of Health and Human Services Food and Drug Administration (FDA) regarding the safety, pharmacokinetics and effectiveness studies of immunoglobulin in primary immunodeficient conditions. According to that guidance document, the optimal number of patients in subgroups for pharmacokinetic assessment (adult patients) ranges from 6 to 12, to obtain a reliable assessment of variability. Considering these recommendations, the number of patients in the cohorts for adult patients was determined as 8–10.

